Significant reform in the way that post-stroke care is delivered is needed. The standard for most inpatient rehabilitation facilities is 3 hours per day spent engaging in one-on-one therapeutic interventions with a therapist. Not only is this approach costly, but new literature partially erodes empirical support for this policy.³¹ A more distributed training approach involving frequent mobilization for shorter periods was associated with better health and function. Conversely more total hours spent in therapy had the opposite effect.^{7,8} Preference for distributed training is consistent with patient perspectives on the necessity of adequate rest during early rehabilitation and animal literature showing that very early intense motor training can be associated with deleterious effects on brain structure and motor function.³²⁻³⁴ Studies also suggest that there may be a critical time window of heightened neuroplasticity within the first few weeks post-stroke that may be bypassed if training does not emphasize neurorestoration (e.g., focuses exclusively on compensatory techniques) $^{35-40}$ and that increasing complex motor activity enhances neurorestoration.⁴¹⁻⁴⁷ Taken together, this literature indicates that frequent short-lived practice with the more affected upper extremity may convey the optimal benefit. Current care does not meet this standard well given that patients remain sedentary for much of the day^{48,49} and have limited opportunities for activity outside of therapy hours. The recommended distributed training approach cannot be easily employed within existing face-to-face treatment models of care due to staffing schedules (therapist tour 7:30-4 on weekdays) and increased documentation burden with distributed face-to-face treatment with a therapist. A potential solution to this problem is to supplement therapist care with technologies that can be utilized independently by patients during idle times of the day.

Another problem with inpatient rehabilitation planning is the paucity of definitive clinical trials to inform the type of motor practice that should be administered. Constraint-Induced Movement (CI) therapy is arguably the most empirically-supported upper extremity intervention in subacute and chronic stroke, with strong evidence of increased effectiveness relative to standard care from the only positive definitively-powered upper extremity trial.^{15,16} Emerging evidence suggests that this is due to CI therapy being the only motor intervention to incorporate behavioral techniques designed to promote carry-over of training from practiced exercises to daily activities.^{23,24,26} These Transfer Package techniques include contracting, daily self-assessment of arm use, and problem-solving. Compared to other high-intensity dose-matched interventions that do not increase arm use for daily activities,²⁵ CI therapy combats learned nonuse, which translates into maintenance of therapeutic gains over time.^{50,51} Given that extent of carryover of motor training to daily activities is strongly associated with improved quality of life (but extent of motor improvement is not).²⁸ the carry-over techniques of CI therapy appear essential to optimal treatment success. The effects of these carry-over techniques in acute stroke have not been well established, however. With the exception of one study,⁵² all studies on acute CI therapy to date ¹⁷⁻ ²² omitted the behavioral strategies that promote carry-over of training, arguably the most essential components of CI therapy. Patient-centered research that seeks to adapt the CI therapy carry-over techniques to the inpatient rehabilitation setting is needed to foster increased acceptance and use of this approach.

Finally, there is the problem of inadequate and disparate continuity of care post-discharge,^{53,54} that particularly adversely impacts rural dwellers and other underserved communities.⁵⁵ Accordingly, function typically declines post-discharge (rather than continues to improve when intensive rehabilitation is available).^{12,13}

Amongst community dwelling individuals with chronic stroke (ongoing multi-site RCT⁷⁶), patient satisfaction with the intervention was high.⁵⁸ Moreover, this system appears superior to standard physiotherapy and is roughly equivalent to in-clinic CI therapy at improving both motor function and

daily arm use (Figure 2), at only a small fraction (<25%) of the cost. The feasibility and efficacy of implementing this low-cost treatment model in an acute care setting has yet to be established, however.

Figure 2: Comparative effectiveness of game-based CI therapy (Grp 3) versus traditional CI therapy (Grp 1) and standard physiotherapy (Grp 4) in an ongoing multi-site RCT (n=41). WMFT=Wolf Motor Function Test; MAL = Motor Activity Log.

Research Design and Methods

The first 3 months of the project will involve participatory action research methods to identify potential barriers to implementation of this new intervention within the VA and to refine the treatment approach to meet the needs of an inpatient population. A half-day focus group $\hat{a}\in \alpha$ -treat $\hat{a}\in \Theta$ will involve at least 3 patients who are currently on the inpatient rehabilitation unit (or recently discharged), their families, and OT/PT/recreational therapy staff. This meeting will serve to finalize the treatment protocol for this study. Areas that will be addressed will include the $\hat{a}\in\alpha$ -dosing $\hat{a}\in \Theta$ schedule for the game-based intervention and needed adaptations to the CI therapy Transfer Package techniques (described below) to promote maximal carry-over from trained activities to everyday use of the weaker upper extremity. Any needed modifications to the technology platform (e.g. data storage) will also be made to comply with the VA $\hat{a}\in^{TM}$ s regulatory policies regarding adoption of new technology.

Setting of Research Study

This study will be conducted at the Minneapolis Veterans Affairs Medical Center (MVAMC). The MVAMC is home to the Stroke Specialty Program (SSP), a CARF accredited program. The SSP tailors rehabilitation for survivors of any stroke mechanism (hemorrhagic, occlusive, etc.) affecting any part of the brain. Services can be adapted for survivors with cognitive challenges. The SSP has averaged 41 admissions in the past three years, though 2017 has projected admissions over 50. Retrospective chart review demonstrates the primary diagnosis resulting from stroke to be hemiplegia in approximately half of the admissions. Most patients (85%) are older than 60 years, predominantly Caucasian (85%) or African-American (10%) and male (98%).

Recruitment: Prospective participants will be screened by a clinician. Patients meeting study criteria will begin the consenting process. We will attempt to recruit twelve subjects each year for a sample of 24. Assuming 20% attrition by 3-month follow-up, we anticipate a sample of 20.

Game-based CI therapy participants will have access to Recovery Rapids and the smart-watch biofeedback app both on the unit and post-discharge and will be exposed to Transfer Package techniques. Recovery Rapids was developed in collaboration with stakeholders and utilizes inexpensive and commercially available gaming/sensor technology (Microsoft Kinectv2) to provide rehabilitation to individuals in their own homes. The Kinect-based game requires users to trigger game actions by performing intuitive movements (gestures) that are characteristic of real-life motor demands.^{56,57} As such, gestures are typically complex and involve both proximal and distal movement (e.g., shoulder flexion with elbow extension and supination). Proximal movements include shoulder flexion/abduction/ adduction and elbow flexion/extension. Distal movements include those that can be reliably detected by the Kinect: forearm supination, grasp/release, and wrist extension. The user utilizes various gestures to paddle a kayak through a river canyon (Fig 1), while collecting hidden treasure, fishing for food, capturing essential supplies that are parachuted down from above, gathering food, solving puzzles, and pulling objects from the river. Bats can attack, river rapids can crash the kayak into the rocks, and low hanging obstacles need to be avoided. To promote adequate dosing, the game utilizes procedural content generation to generate infinite novel content. This game-based rehabilitation incorporates elements of constraint-induced movement (CI) therapy, including shaping (progressively increasing the difficulty of required motor movements as a patient obtains mastery) and rapid customizability to the preferences/needs of the therapist and client. To accomplish shaping, a gesture library for each of the 10 possible complex movements consists of multiple difficulty levels, each progressing in the range of motion that must be exerted at a particular joint to trigger the desired game mechanic. More complex gestures have up to 25 different levels of difficulty. The gaming technology to be employed here $\hat{a} \in \alpha$ learns $\hat{a} \in \Phi$ what the user is capable of and self-calibrates the difficulty of the movements to the clientâ€[™]s level of ability within 30 minutes of therapist-supervised game play. This means that it will no longer respond to poorer movement mechanics than the user is capable of. This means that when a client engages in unsupervised practice, the game will only respond to movements executed according to the movement mechanics that a therapist taught in-session, implicitly preventing weaker attempts. The game also continues to update these difficulty settings as a user displays improvement.

Participants will begin playing the Recovery Rapids game when clinically appropriate per the clinician, at least 1 week prior to discharge. We anticipate at least three sessions with an OT will be devoted to teaching the game and personalizing game play to the individual. Though the exact dosing schedule will be refined based on stakeholder feedback gathered during preparatory work, game play will then occur independently outside of OT/PT sessions. Study clinicians will determine how often participants should engage in the game, with a general recommendation being 10-minute periods three times per day with the possibility for more gameplay on weekends. Recreation therapy staff will assist participants with game setup as needed. Participants will be asked to track how much time they spend on the game. Study clinicians will engage in adherence strategies that are typically used clinically with the participant to enhance use of the gaming system as needed.

Participants will have the option of wearing smartwatches (Figure 3) on both upper extremities targeting a wearing schedule of: all waking hours during the inpatient stay and 3-month follow-up. An app on the smart-watch uses accelerometer hardware to record the number of movements performed. The app also enables notifications (vibration coupled with $\hat{a} \in \mathbb{C}$ Please use me $\hat{a} \in \mathbb{C}$ text prompt) if the arm is not utilized for a period of 10 minutes. Notification will be set to $\hat{a} \in \mathbb{C}$ for the weaker arm and $\hat{a} \in \mathbb{C}$ for the stronger arm.

Figure 3: Smart-watch Biofeedback device.

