discharge. Motor function will be assessed prior to treatment, before discharge, and at 3 monthsâ \in^{TM} follow-up by an OT. The primary outcome will be improvement on the Action Research Arm Test at post-treatment. The ARAT measures the time to complete standardized UE movements, with established reliability and validity. ⁶⁰⁻⁶³ Secondary measures of impairment, quality of life, and satisfaction with the gaming system may include the Wolf Motor Function Test (WMFT), Fugl-Meyer ⁶⁴⁻⁶⁷, Neuro-QoL⁶⁸⁻⁷⁰, and the Quebec User Evaluation of Satisfaction with assistive Technology (QUEST) respectively.

Statistical Analysis: Statistical analysis will be jointly led by our off-site collaborator [name] and the VA biostatistician. We plan to compare therapy induced changes in motor function (ARAT) and potentially motor impairment (Fugl Meyer), UE function (WMFT), and quality of life (Neuro-QoL) via mixed effects linear models or non-parametric equivalents will be used. We plan to examine outcome measure scores over time using graphical means. Statistical testing will be used to determine whether individuals lost to follow-up differ from those who completed the study.

Timeline: Institutional Review Board (IRB) review will be completed after funding is confirmed and before receipt of funding. Two-four patients per quarter will be recruited, with recruitment completing by month 19. The next 3 months will involve final follow-up data collection. The final 3 months will involve data analysis and publication preparation.

rable 2. Froposed Froject Ennemie								
Effect of Constraint-Induced Gaming Therapy in an			Q3	Q4	Q5	Q6	Q7	Q8
Acute Care Setting								
Participatory Action Research Methods								
Identify Ideal Implementation of Gaming CI Therapy								
Work with Tech Transfer								
Data Acquisition & Follow-up								
Data Processing and Analysis								
Annual and final reports to VA RR&D Service								
Dissemination of knowledge gained during the project								

Table 2. Proposed Project Timeline

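### The stated sample of 24 needs 24 months at twelve per year, but recruitment closes by month 19, which gives about 18–19 enrolled and 14–15 at 3 months

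*Combined protocol and SAP*

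**What the plan says.** The Recruitment paragraph (Setting of Research Study) gives the only sample-size figures for the prospective group: "We will attempt to recruit twelve subjects each year for a sample of 24", followed by "Assuming 20% attrition by 3-month follow-up, we anticipate a sample of 20".

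The Timeline paragraph, after Statistical Analysis, sets the calendar: "Two-four patients per quarter will be recruited, with recruitment completing by month 19". It then gives the remaining time to other work: "The next 3 months will involve final follow-up data collection" and "The final 3 months will involve data analysis and publication preparation". Table 2 lays the project out over eight quarters (Q8 is the last column).

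Research Design and Methods puts preparatory work first: "The first 3 months of the project will involve participatory action research methods to identify potential barriers to implementation". Of the focus-group meeting held in that period it says "This meeting will serve to finalize the treatment protocol for this study". The description of game play also depends on that work: "Though the exact dosing schedule will be refined based on stakeholder feedback gathered during preparatory work".

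**The concern.** The annual rate and the closing month are both current text, and they do not produce the same number of patients. Twelve a year for 24 patients assumes two full years of enrolment. The Timeline allows at most 18 or 19 months, because the last six months of an eight-quarter project are given to follow-up and analysis. Nothing in the document reconciles the two.

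The figures 24 and 20 are all a reader has for judging what this pilot will deliver, and feasibility is part of Aim 2. As written, nobody can say whether 18 enrolled patients would meet the plan or fall short of it. The stakes stop there: no power target, interval width or progression criterion is set on these numbers, so no analysis result changes.

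**Working it through.** **Inputs**
- Rate: 12 per year (Recruitment) = 1 per month = 3 per quarter. This is also the midpoint of the Timeline's two to four per quarter.
- Target: 24 enrolled, 20% attrition, 20 at 3 months (Recruitment).
- Close: by month 19, then 3 + 3 months (Timeline); eight quarters = 24 months (Table 2).
- Preparatory phase: first 3 months (Research Design and Methods).

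**The plan's own figures.** 12 per year × 2 years = 24. 24 × 0.80 = 19.2, close to the stated 20; the difference is rounding and is not the issue here. Both figures reproduce, but only with a 24-month recruitment window.

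**Window.** Two closing points are carried. Closing at month 18 gives 18 + 3 + 3 = 24 months, which fits eight quarters. Closing at month 19 gives 19 + 3 + 3 = 25.

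**Formulas.** Enrolled = quarterly rate × recruitment months ÷ 3. At 3 months = enrolled × 0.80.

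| Opens | Closes | Recruitment months | Enrolled / at 3 months, 3 per quarter | Enrolled / at 3 months, 4 per quarter | Rate per quarter needed for 24 |
|---|---|---|---|---|---|
| Month 1 | 18 | 18 | 18 / 14.4 | 24 / 19.2 | 4.00 |
| Month 1 | 19 | 19 | 19 / 15.2 | 25.3 / 20.3 | 3.79 |
| Month 4 | 18 | 15 | 15 / 12.0 | 20 / 16.0 | 4.80 |
| Month 4 | 19 | 16 | 16 / 12.8 | 21.3 / 17.1 | 4.50 |

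At the floor of 2 per quarter from month 1, enrolment is 12.0 or 12.7, so the Timeline's full range from month 1 is about 12–25.

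**Share of the target at 12 per year.** From month 1: 18/24 = 75% and 19/24 = 79%. From month 4: 15/24 = 63% and 16/24 = 67%.

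**Time needed to keep 24 at 12 per year.** Opening in month 1, recruitment ends in month 24 and the project in month 24 + 3 + 3 = 30. Opening in month 4, recruitment ends in month 27 and the project in month 3 + 24 + 3 + 3 = 33. The schedule has 24.

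**The case against.** The strongest reply is that the Timeline gives a range, and its upper end works: 4 per quarter from month 1 yields 24–25 enrolled and 19–20 at 3 months, essentially the stated figures. That is true, and the shortfall should be described as one at twelve per year. But it needs 3.8–4.0 per quarter throughout, about 15–16 per year, which exceeds the Recruitment paragraph's own rate. If the preparatory quarter comes first, even 4 per quarter gives only 20–21 enrolled.

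The site's volume does not exclude the ceiling. Reading the 41 to 50 admissions as annual, with about half hemiplegic, gives roughly 20–25 candidates a year. Sixteen a year would be about 64–78% of them (16/25 to 16/20.5), before eligibility limits such as residence and a home screen. That is demanding, though not impossible.

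Reading the rate as twelve per project year does not help. The second year then has only 6–7 recruitment months, which at 4 per quarter is 8–9 patients.

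The section on human subjects involvement allows further recruitment when a participant leaves. It gives no number and no extra time, so replacements must fit the same window.

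Two points stand. The month-4 opening is an inference: no readable text gives the first enrolment month, and the quarter markings in Table 2 cannot be read. And this is a pilot that words its target as an attempt, so the consequence is modest.

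**Conclusion.** The concern holds. The stated rate and the stated recruitment window do not deliver the stated sample. At twelve per year from month 1, expect 18–19 enrolled and about 14–15 at 3 months, against 24 and 20: a shortfall of 5–6 enrolled. This assumes steady accrual, the plan's 20% attrition, and a close at month 18 or 19. It does not depend on the month-4 opening; if that opening is right, the shortfall is 8–9 enrolled, with about 12–13 at 3 months.

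The 3-month figures count completers. The number with an Action Research Arm Test before discharge could be closer to the number enrolled. The plan should correct the forecast, but no planned analysis is invalidated.

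**What to change.** State one recruitment rate with its opening and closing months, use it in Research Design and Methods, Recruitment and Timeline alike, and give the expected sample that follows from it.

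- At twelve per year, opening in month 1: about 18–19 enrolled and about 14–15 at 3 months.
- At twelve per year, opening in month 4: about 15–16 enrolled and about 12–13 at 3 months.
- If 24 is kept: about 19 at 3 months, with the rate or window it requires. That is 3.8–4.0 per quarter from month 1; 4.5–4.8 per quarter from month 4, which is above the stated range; or twelve per year to month 24 or 27.

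Restating the sample costs only wording and a less favourable headline number; no extra patients are needed. Keeping 24 changes conduct: either faster enrolment, or at twelve per year a project of about 30 months (opening in month 1) or 33 months (opening in month 4).

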- 3) 18 hours independent game play is encouraged following discharge (30 min, 3 times weekly) over and above standard care (will be documented as covariate)
- 4) Use of smart watch with biofeedback

Retrospective Chart Review: We will conduct a chart review of Veterans who have participated in inpatient stroke rehabilitation at the Minneapolis VA over the past 5 years. Veterans whose charts will be reviewed will be identified by clinician members of the study team. We will review the medical records of each Veteran using CPRS and extract the relevant data. This will include demographic data (e.g. age, diagnosis, location, etc.), clinical data (e.g. outcome measures, interventions provided) and may include other clinical information as needed to adequately describe our sample. Data pulled from Veteran charts will be used as a retrospective control for the participants who receive the study intervention.

Approach to Aim 1: Determine the extent to which game-based CI therapy increases use of the more affected upper extremity from inpatient rehabilitation through subacute follow-up. For participants who use the smartwatch app, arm use will be tracked via a smart-watch app (see above) during the inpatient stay and post-discharge. Smart-watch biofeedback notifications for the standard care group will be set to $\hat{a} \in \hat{c} = \hat{a} \in \hat{c}$ for the weaker arm and $\hat{a} \in \hat{c} = \hat{a} \in \hat{c}$ for the stronger arm. Missing data (e.g., participant forgot to put the watch on one day) will be interpolated from data obtained during compliant days. The primary repeated-measures outcome will be total movement counts for each 1-week epoch from baseline through 3 months post-discharge (~12 weeks).

Approach to Aim 2. Pilot the clinical effectiveness and feasibility of distributed gaming CI therapy for improving motor function of the more affected upper extremity at 3 months post-

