For Community Based Participatory Model, study participants (least 3 patients who are currently on the inpatient rehabilitation unit or recently discharged, their families, and OT/PT/recreational therapy staff) will offer suggestions and feedback related to design of a video game-based rehabilitation program. Their opinions may be recorded via audio recording and/or video recording. Audio/video recordings will be kept confidential. This may involve a focus group discussion or one-to-one interview. Participants will aid in developing study-related treatments. This may include informing the treatment schedule for the intervention, advising the outcome measures of most importance to them, and helping refine study-related forms. Through collaborating with people who have personally experienced the challenge of stroke recovery, we hope to develop more patient-centered and relevant interventions.

For the Trial proposed, Veterans with upper extremity hemiparesis due stroke in the brain (including brainstem) are the focus of this study. The subjects, males and females of all races and ethnic origins, are expected to be between 18 and 88 years old. There are no targeted populations for this study. The study will recruit Veterans with acute hemiparesis resulting from injury to the brain due to stroke (including brainstem) as inpatients at the Minneapolis VA Health Care System and who meet all the inclusion criteria and none of the exclusion criteria, regardless of race, sex, or ethnicity. Vulnerable populations will not be targeted. There will be no children participating in this study. Inclusion and exclusion criteria are indicated in the table below.

Inclusion	Exclusion
Veterans between 18 and 88 years of age	Complete loss of arm function
Inpatient at the Minneapolis VAHCS.	No contact address or telephone
Willing and able to give Informed Consent or meets criteria for surrogate consent	Active substance use disorder or Major uncontrolled psychiatric disorder
Upper extremity hemiparesis resulting from stroke in the brain (including brainstem) or tumor resection at the discretion of the therapist.	
Lives within vicinity of the Minneapolis VA	
Has either a computer monitor or TV at home the participant will allow the gaming device to be connected to.	

Table 3. Inclusion and Exclusion Criteria

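### Treated patients must stay at least a week after game play starts but chart controls have no minimum stay, so the discharge ARAT comparison is open to length-of-stay selection of unknown direction

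*Combined protocol and SAP*

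**What the plan says.** **Treated group.** Research Design and Methods, in the description of the game intervention: "Participants will begin playing the Recovery Rapids game when clinically appropriate per the clinician, at least 1 week prior to discharge". Table 3 carries no such condition. Its only entry on inpatient status is "Inpatient at the Minneapolis VAHCS". The plan does not say how an enrolled patient who is discharged sooner is handled.

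**Controls.** The Retrospective Chart Review paragraph gives the source as follows: "We will conduct a chart review of Veterans who have participated in inpatient stroke rehabilitation at the Minneapolis VA over the past 5 years". On selection: "Veterans whose charts will be reviewed will be identified by clinician members of the study team". On their role: "Data pulled from Veteran charts will be used as a retrospective control for the participants who receive the study intervention". No minimum stay, matching rule or shared eligibility rule is given.

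**Outcome.** Approach to Aim 2: "The primary outcome will be improvement on the Action Research Arm Test at post-treatment". The aim itself refers to 3 months after discharge. Assessments are at baseline, before discharge and at 3 months.

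**Analysis.** The Statistical Analysis paragraph names mixed effects linear models or non-parametric equivalents. It names no term for length of stay or for days between assessments. The only item marked as a covariate is in the line of Table 1 on game play after discharge.

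**The concern.** One group is defined partly by a future event, still being an inpatient a week after play starts. The other is not. A patient discharged on day 6 can enter as a chart control but could not have been treated as the rule is written. Applying Table 3 to the charts would not cure this, because the stay condition is not in Table 3.

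The interval from baseline to discharge is set by length of stay, which is the quantity cut off in one group only. A longer interval means more therapy days and more natural recovery, so the two groups could differ in ARAT change with no effect of the game. If short-stay patients are the fast recoverers, leaving them out of one group could act the other way. The plan presents this pilot as the source of initial efficacy evidence before a definitive trial, so a distorted contrast would carry forward.

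**Working it through.** The plan gives no figure on this point and no distribution of stay, so the calculation is an illustration over stated assumptions.

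**Inputs from the documents**
- Minimum stay after the start of play: 7 days.
- Inpatient period: weeks 1 to 3 in Table 4. Table 1 and the weekly game time agree: 10.5 h / 3.5 h per week = 3 weeks. This prompts a mean stay of 21 days.
- Treated sample: 24 recruited. 24 × 0.80 = 19.2, which the plan gives as 20.

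**Assumptions**
- Stay L follows a gamma distribution with mean 21 days, SD 7, 10 or 14, and a 2-day floor.
- Play starts on day S = 2, 5, 7 or 10.
- Recovery is exponential with time constant τ = 14, 28 or 42 days, and there is no treatment effect.
- The rule acts as an exclusion: treated patients have L ≥ S + 7, while controls are all patients.
- This makes 3 × 4 × 3 = 36 settings, with 400,000 simulated stays each. The central case is SD 10, S = 5.

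**Step 1. Both baselines at admission.** Gain = 1 − exp(−L/τ). In the central case 18% of patients are removed from the treated group only, and mean stay is 23.7 against 21.0 days, a difference of 2.7. At τ = 28 the mean gains are 0.551 and 0.500, and 0.551 / 0.500 = 1.10.

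**Step 2. Treated baseline at the start of play, control baseline at admission.** Treated gain = exp(−S/τ) − exp(−L/τ). At S = 5 and τ = 28, the recovery before baseline is 1 − exp(−5/28) = 0.164. Then (0.551 − 0.164) / 0.500 = 0.77, about 23% lower.

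**Step 3. Outcome at 3 months after discharge, baselines at admission.** Gain = 1 − exp(−(L + 90)/τ).

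| Comparison | Central case, τ 14 to 42 | All 36 settings |
|---|---|---|
| To discharge, both baselines at admission | +8% to +11% | +0.8% to +37.4% |
| To discharge, treated baseline at start of play | −33% to −19% | about −60% to +2%, all but one negative |
| To 3 months, both baselines at admission | 0% to +0.5% | at most +1.7% |

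Across the 36 settings the rule removes 2% to 47% of patients.

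**Step 4. Sensitivity of the first row** (S = 5)
- τ = 28, mean stay 16 days (SD 8): +20.8%.
- τ = 28, mean stay 28 days (SD 12): +3.1%.
- Central case, with τ rising with the square root of stay: +5.6%.
- Central case, with the amount of recovery falling with the square root of stay: +4.0%.

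**Step 5. Effect on a test.** Let f be the share of short-stay controls and d the difference in mean change between long-stay and short-stay patients, in SD units. Bias = f × d. Neither is in the documents.
- With f = 20% and d = 0.5, bias = 0.10 SD.
- With 20 treated and 102 controls, SE = √(1/20 + 1/102) = 0.245 SD, and a nominal 5% two-sided test rejects 6.9% of the time. With 20 against 20 it rejects 6.2%.
- Over f = 10% to 40% and d = 0.25 to 1.0, the rejection rate is 5.1% to 37% (20 against 102) or 5.1% to 24% (20 against 20).

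**The case against.** **The one-week line is a timing rule.** It sits in the intervention description, not in Table 3, and nothing says a patient discharged sooner leaves the treated group. This stands. The asymmetry follows only if the rule is applied as written. It does not dispose of the point, because the plan gives no handling for such patients.

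**The direction is not established.** A reader might infer that the rule pushes the comparison towards the game. That needs both baselines at admission. The plan places the treated baseline before treatment, and Table 4 puts it in week 0 with game set-up in week 1. Where this falls relative to admission is not settled, nor is the control baseline. Step 2 shows that an unaligned baseline can outweigh the stay rule and reverse the sign.

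**The endpoint may be 3 months.** Aim 2 speaks of 3 months after discharge, and at that time the bias is negligible in this model. This stands, and it limits the point to change up to discharge. However, the primary outcome is placed at post-treatment, and the charts are not promised a 3-month ARAT.

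**The actual control set may be narrower.** Clinicians identify the charts, and a change score needs two ARATs, so very short stays may drop out. That is possible, but no rule says so.

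**The broader gap is the control definition.** Time zero and eligibility are both missing for the charts. This is fair, and the fix therefore has to cover time zero as well as the minimum stay.

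**Conclusion.** The asymmetry is in the text and nothing in the plan removes it. Following the plan as written compares groups with different stay distributions, and the ARAT change from baseline to discharge is exposed to that.

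The documents do not give the size or the sign. The +1% to +37% range (central +8% to +11%) rests on a 21-day mean stay, the assumed spreads, start days and recovery curves, and baselines at admission in both groups. The sign turns negative in nearly all settings when the treated baseline moves to the start of play.

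A reader might infer that short-stay patients can sit only in the control group and that the game is therefore favoured. The documents support neither as a certainty: the handling of early discharges is unstated, and the direction depends on baseline timing and on why patients leave early. The point is a repairable design gap, not a demonstrated bias in a known direction.

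**What to change.** In Retrospective Chart Review:

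1. Define the same time zero for both groups: the routine ARAT nearest the actual start of play for treated patients, and nearest an assigned landmark day for controls. The landmark day could be the treated group's median start day, counted from the first routine ARAT.
2. Keep only controls who were still inpatients at least 7 days after the landmark.
3. State that enrolled patients discharged sooner stay in the treated group for a sensitivity analysis against the unrestricted charts.
4. Report length of stay and days between ARATs in both groups. Adjust for days between ARATs only as a sensitivity analysis, since recovery and treatment can both affect it.

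The start rule for game play is not changed.

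**Cost.** The work is a chart-selection rule using dates in the medical record. Reading the 41 admissions as a yearly figure, the pool is about 41 × 5 × 0.5 = 102 charts with hemiplegia. If 10% to 40% are short-stay (assumed), 92 to 62 remain. With 20 treated patients the SE rises from 0.245 SD to √(1/20 + 1/92) = 0.247 or √(1/20 + 1/62) = 0.257. The result then applies to patients with at least that stay. The documents list ARAT among routine OT evaluations but not how often it is repeated, so the number of charts with usable pairs must be checked first.
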